1.0 STUDY OBJECTIVES

To evaluate the ocular safety and efficacy of topical administration of ISV-305 (0.1% dexamethasone in DuraSite 2) compared to vehicle when dosed BID for 14 days in subjects diagnosed with blepharitis.

2.0 OVERALL STUDY DESIGN

This study is a Phase 3, randomized, multicenter, double-masked, vehicle-controlled, parallel-group clinical study. Patients \geq 1 year of age diagnosed with active, symptomatic blepharitis (e.g., flare-up) will be enrolled.

Prior to enrollment, the study will be discussed with prospective subjects, and those wishing to enter will be asked to give written informed consent. For subjects who, according to local regulations, have not yet reached the age of majority, the subject's parent(s) or legally authorized representative must sign the Informed Consent Form (ICF) and the minor's written assent will be obtained according to the local requirements.

Once informed consent has been obtained, the subjects will be questioned regarding their medical history to determine whether or not they are in satisfactory health to enter the study and to determine if they meet the specific entry criteria.

Clinically-diagnosed, active, symptomatic blepharitis (e.g., flare-up) is defined by a minimum combined score of 6 for the following signs and symptom in at least one eye, with a minimum score of 2 for eyelid redness, and a minimum score of 1 for eyelid irritation.

- 1) Eyelid redness
- 2) Eyelid swelling
- 3) Eyelid debris
- 4) Eyelid irritation

Subjects meeting all entry requirements will be asked to use lid scrubs for at least 7 days prior to Day 1, and will then be reassessed for eligibility prior to being randomized into the study. Subjects still meeting the entry criteria will be randomized into the study and begin a 14-day dosing phase (Day 1 – Day 14) followed for approximately 2 weeks during the follow-up phase (Day 15 – Day 29). Five visits will be required for full study participation: Screening Visit (Day -10 to Day -7), Rescreening/Randomization/Dosing visit (Day 1), Dosing visit (Day 7), and the Follow-up visits (Day 15 and Day 29).

Approximately 550 evaluable subjects with blepharitis will be randomized into the study in a 2:1 ratio: ISV-305: approximately 366 subjects and vehicle: approximately 184 subjects.

Some subjects may have both eyes qualify for the study. In these cases, data from the eye with the highest combined clinical signs and symptoms score on Day 1 will be designated by the investigator as the study eye and analyzed for efficacy.

Subjects (or parent or caregiver for subjects too young or otherwise unable to self-apply the IP) will be instructed to self-apply their first dose of IP at the study site on Day 1, and will receive instructions for dosing at home and completing a dosing diary, to be used as a memory aid.

Subject safety will be evaluated throughout the study. The safety parameters to be assessed are the incidence of AEs and SAEs, discontinuations due to AEs, changes in best corrected visual acuity (BCVA) and IOP, and biomicroscopic and ophthalmoscopic findings.

Efficacy will be assessed by biomicroscopic measurement of the clinical improvement in signs of eyelid swelling, eyelid redness, eyelid debris, and subject-reported symptom of eyelid irritation. Improvement is defined as a reduction in baseline signs and symptoms score by at least 2 units by Day 15 with no worsening of any sign or symptom. Other secondary efficacy analyses will be performed as outlined in the statistical analysis plan (SAP).

3.0 SELECTION AND WITHDRAWAL OF SUBJECTS

3.1 Number of Study Subjects

The study will enroll approximately 550 subjects \geq 1 year of age with active, symptomatic blepharitis (e.g., flare-up). Subjects will be enrolled in the US.

3.2 Inclusion Criteria

The following are inclusion criteria for prospective study subjects to be confirmed at the Screening Visit 1 (Day -10 – Day -7) and reconfirmed prior to randomization at Visit 2 (Day 1). The sponsor will not grant any protocol eligibility waivers.

- a. Have a clinical diagnosis of active, symptomatic blepharitis (e.g., flare-up) defined by a minimum combined score of 6 for the following signs and/or symptoms in at least one eye, with a minimum score of 2 for eyelid redness, and a minimum score of 1 for eyelid irritation:
 - 1) Eyelid redness
 - 2) Eyelid swelling
 - 3) Eyelid debris
 - 4) Eyelid irritation
- b. Are \geq 1 year of age at Screening Visit (-10 to Day -7, Visit 1) of either sex and any race.
- c. Signature of the subject or parent(s) or legally authorized representative on the ICF, and when appropriate the minor's assent in accordance with local regulations.

- d. Are willing and able to follow all instructions and attend all study visits. This applies to parent or caregiver for subjects too young or otherwise unable to self-apply the IP.
- e. Are willing to avoid disallowed medication for the duration of the study.
- f. If female is of childbearing potential, agree to and submit a urine sample for pregnancy testing (prior to enrollment and at the end of the study), and use effective contraception for the duration of the study.

Male subjects whose female partners are not post-menopausal must agree to one of the following: 1) completely abstain from sexual intercourse, 2) use a barrier method (condoms) with spermicide during sexual intercourse for the duration of the study, 3) provide documentation for having had a vasectomy (with documented infertility).

- g. Have an intraocular pressure (IOP) > 8 mmHg and \leq 22 mmHg in either eye.
- h. Have used non-prescription lid scrubs for at least 7 days prior to Day 1 (Visit 2) and willing to continue lid scrub use throughout the duration of the study. Prescription lid scrubs are disallowed.

3.3 Exclusion Criteria

The following are exclusion criteria for prospective study subjects to be confirmed at the Screening Visit 1 (Day -10 – Day -7) and reconfirmed prior to randomization at Visit 2 (Day 1). The sponsor will not grant any protocol eligibility waivers.

- a. Have known sensitivity or poor tolerance to any component of the IP.
- b. Have had eyelid surgery in the study eye within twelve (12) months prior to the Screening visit (Day -10 to -7, Visit 1) or plan to have eyelid surgery during the study that, in the investigator's opinion, would interfere with the study parameters.
- c. Have an acute ocular infection (bacterial, viral or fungal) or active ocular inflammation other than blepharitis in the study eye.
- d. Are currently suffering from moderate or severe Dry Eye in the study eye.
- e. Have used prescription medication lid scrubs within 4 weeks prior to dosing and/or plan to use them throughout the 14-day dosing period of the study.
- f. Have used topical medications on the eyelids or topical ophthalmic corticosteroid medications or systemic use of a corticosteroid medication within 14 days prior to dosing and/or plan to use them throughout the duration of the study. Stable use (greater than one month prior to dosing of an unchanged dose) of inhaled or nasal corticosteroids, topical

dermal corticosteroid or antibiotic medication (except on the eyelids), or glaucoma eye medication is allowed.

- g. Have used tear substitutes (e.g., artificial tears) within 2 hours prior to dosing and/or plan to use them throughout the 14-day dosing period of the study.
- h. Use of any eye make-up (including lid skin, lid margins, and lashes) during the 2-week dosing period of the study.
- i. Have had a micropigmentation (permanent eye makeup) procedure on the eyelid skin within 4 weeks prior to dosing, or plan to have such a procedure during the study.
- j. Be currently pregnant, nursing, or planning a pregnancy, or be a woman who has a positive pregnancy test.
- k. Have any uncontrolled systemic disease or debilitating disease (e.g., cardiovascular disease, hypertension, diabetes, or cystic fibrosis).
- l. Have any clinically significant cardiovascular disorders (e.g., unstable angina, myocardial infarction or cerebrovascular accident within the past six months, Class III or IV congestive heart failure, ventricular arrhythmias).
- m. Have any history of liver or kidney disease resulting in persisting dysfunction that, in the investigator's opinion, would interfere with the study parameters.
- n. Have clinically significant lash or lid abnormality other than blepharitis (e.g. trichiasis, entropion or ectropion) in the study eye.
- o. Are currently suffering from alcohol and/or drug abuse.
- p. Have prior (within 30 days prior to dosing) or anticipated concurrent use of an investigational drug or device.
- q. Have a condition or a situation which, in the investigator's opinion, may put the subject at increased risk, confound study data, or interfere significantly with the subject's study participation.
- r. Use of any medication the investigator feels may interfere with the study parameters.

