4.2 Instructions for Use and Administration

Subjects will be randomly assigned to receive either ISV-305 or vehicle which will be administered BID to the closed study eyelid and if needed to the closed non-study eyelid along the eyelash line as a topical ophthalmic: 1 drop per eye in the morning and 1 drop per eye in the evening for 14 days. Subjects (including parent and/or caregiver) will be instructed to smear 1 drop of IP to the closed study eyelid along the eyelash line on Day 1 at the study site upon randomization and 1 drop in the evening, and to continue dosing BID at approximately 12-hour intervals for a total of 14 days. Subjects will then be followed for an additional 15 days. Subjects will be given a dosing diary to record IP application times, and will be questioned to determine if they have followed the dosing schedule.

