5.0 CONTRAINDICATIONS, WARNINGS AND PRECAUTIONS

Contraindications, warning and precautions for ophthalmic dexamethasone as described in the labeling of the approved product Maxidex (0.1% dexamethasone) are presented below.

Use of ophthalmic dexamethasone is contraindicated in epithelial herpes simplex (dendritic keratitis), vaccinia, varicella, and most other viral diseases of the cornea and conjunctiva, tuberculosis of the eye and fungal disease of ocular structures.

Class warnings for corticosteroids such as dexamethasone are well known and state that prolonged use may result in ocular hypertension and/or glaucoma, with damage to the optic nerve, defects in VA and fields of vision, and posterior subcapsular cataract formation. Prolonged use may also suppress the host response and thus increase the hazard of secondary ocular infections. In diseases causing thinning of the cornea or sclera, perforations have been known to occur with the use of topical corticosteroids. In acute purulent conditions of the eye, corticosteroids may mask infection or enhance existing infection. It is recommended that if corticosteroids are used for 10 days or longer, intraocular pressure should be routinely monitored even though it may be difficult in children and uncooperative patients.

The possibility of persistent fungal infections of the cornea should be considered after prolonged corticosteroid dosing.

Subjects are excluded from participating in the study if there is known hypersensitivity or poor tolerance to any component of the IP or any of the procedural medications such as anesthetic and/or fluorescein drops, dilating drops, etc. See Exclusion Criterion a.

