6.2 Examination Procedures

The following ophthalmic examinations will be conducted at intervals specified in Table 1 Schedule of Assessments.

- **Clinical Signs and Symptom:** The clinical signs of blepharitis: eyelid redness, eyelid swelling and eyelid debris will be evaluated at every visit and will be scored by the investigator using a 0-3 grading scale. The subject symptom of eyelid irritation will also be evaluated at every visit and graded by the subject using a 0-3 grading scale.
- **Best Corrected Visual Acuity (BCVA):** BCVA will be measured at every visit. The Early Treatment Diabetic Retinopathy Study (ETDRS) log of the minimum angle of resolution (logMAR) will be used to measure BCVA. As appropriate, Lea Symbols® will be used in children.
- **Intraocular Pressure (IOP):** IOP will be measured in mmHg using an applanation tonometer at every visit. IOP is to be measured in all subjects.
- **Ophthalmoscopy:** Ophthalmoscopy will be performed by a board-certified ophthalmologist at Day -10 to -7 (Visit 1) and Day 15 (Visit 4) or Day 29 (Visit 5) if not completed at Visit 4.
- **Biomicroscopy:** Slit lamp biomicroscopy will be performed at every visit during the study to observe the overall health of the eye, including the lid/lashes, conjunctiva, cornea anterior chamber, iris, and lens. Any observations at the screening visit should be recorded as ocular medical history, and any new or worsened observations may be recorded as AEs. Slit lamp biomicroscopy will be conducted by a board-certified ophthalmologist at every visit.

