8.1.3 Safety Endpoints

- Incidence of ocular adverse events and serious adverse events
- Incidence of non-ocular adverse events and serious adverse events
- Measurement/evaluation and change from baseline at each scheduled visit for the following ocular-specific parameters:
 - Best corrected visual acuity (BCVA)
 - Intraocular pressure (IOP)
 - Slit-lamp biomicroscopy
 - Ophthalmoscopy findings

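### Exclusion c protects only the study eye from dosing over infection or other inflammation, while Section 4.2 lets the steroid go on the other eyelid with no condition on that eye

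*Protocol*

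**What the plan says.** Exclusion c in Protocol Section 3.3 rules out subjects who "Have an acute ocular infection (bacterial, viral or fungal) or active ocular inflammation other than blepharitis in the study eye". It is to be confirmed at Visit 1 and again before randomization on Day 1.

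Section 4.2 has the product "administered BID to the closed study eyelid and if needed to the closed non-study eyelid along the eyelash line", one drop per eye morning and evening for 14 days. It does not say what makes dosing of the second eye necessary, or what would rule it out. Table 1, footnote 1, lists eyes dosed with product separately from the study eye, so dosing beyond the study eye is planned. Section 4.1 gives the active product as 0.1% dexamethasone.

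Where both eyes qualify, Section 2.0 says that "the eye with the highest combined clinical signs and symptoms score on Day 1 will be designated by the investigator as the study eye".

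Section 5.0 sets out the labelled contraindications of ophthalmic dexamethasone. After herpes simplex keratitis, vaccinia and varicella it lists "most other viral diseases of the cornea and conjunctiva, tuberculosis of the eye and fungal disease of ocular structures". It also warns: "In acute purulent conditions of the eye, corticosteroids may mask infection or enhance existing infection". Neither statement is limited to one eye. The only exclusion criterion that Section 5.0 refers to is a, on sensitivity to the product.

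**The concern.** An exclusion tied to a drug's contraindications should cover every eye that receives the drug. Exclusion c is the entry criterion closest to Section 5.0, and on its plain reading it follows the analysed eye and not the dosed eyes.

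What is at stake is the safety of the fellow eye. A steroid could be given twice daily for two weeks to an eye in which the protocol's own safety text advises against it. Sites are masked, so they cannot tell which fellow eyes receive dexamethasone and which receive vehicle. Worsening in such an eye would also enter the safety endpoint worded as "Incidence of ocular adverse events and serious adverse events" (Protocol Section 8.1.3), which is not restricted to the study eye.

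**Working it through.** The plan gives no figure to reproduce here. The check sets the entry rule against the dosing rule.

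**1. Which eyes each rule covers**

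| Text | Eyes covered |
|---|---|
| Section 3.3, exclusion c | study eye (plain reading) |
| Section 4.2, dosing | study eye, plus the non-study eye where needed |
| Section 5.0, contraindications and warnings | no limit to one eye |

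The dosing rule reaches an eye that the entry rule does not.

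**2. A worked case.** A subject has blepharitis that qualifies in both eyes and an acute viral infection in one. Section 2.0 makes the higher-scoring eye the study eye.
- If the infected eye scores higher, it is the study eye and c excludes the subject.
- If the infected eye scores lower, it is the fellow eye. On the plain reading c does not exclude the subject, and Section 4.2 does not bar dosing that eye.

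Eligibility under c then depends on which eye scores higher, not on whether the infected eye will be dosed. There is also a timing problem. When both eyes qualify, the study eye is chosen on the Day 1 score, so at Visit 1 the site does not yet know which eye c refers to.

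**3. The other reading of c.** The closing words may qualify only the second part, on inflammation. Infection in any eye would then be excluded, and the viral case above would be caught. Replace the infection with another active inflammation and the case still gets through. The gap is narrower on this reading but remains.

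**4. Whether another provision closes the gap**
- Criterion q excludes a condition that, in the investigator's opinion, "may put the subject at increased risk, confound study data, or interfere significantly" with participation. It can reach the fellow eye, but only by judgement.
- Section 4.2 makes fellow-eye dosing conditional on need, but need is not defined and no reason to withhold is given.
- Section 6.2 states: "Slit lamp biomicroscopy will be conducted by a board-certified ophthalmologist at every visit". This may detect disease, but no text provided says to withhold product from that eye. Table 1, footnote 1, allows some procedures in the study eye only and does not say which.

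Each lowers the likelihood. None is a rule for the fellow eye.

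**5. Size.** Exposure of one such eye follows from Section 4.2: 2 drops per day × 14 days = 28 drops at most. About 366 of 550 subjects (366 / 550 = 67%) are allocated to dexamethasone. The number affected would be 550 × (share dosed in the fellow eye) × (share of those with a relevant condition in that eye only). The documents give neither share, so no count is offered.

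**The case against.** The strongest reply is that several controls already reach the fellow eye. Section 5.0 is protocol text, and treating an eye with viral or fungal disease would contradict it. For harm to occur, an ophthalmologist at the slit lamp would have to see the disease, set Section 5.0 aside, not use criterion q, and still decide that the eye needs product. This stands as a reason to think the event rare. It does not supply the missing rule. Section 5.0 presents the labelling of an approved product and turns it into an entry criterion only for sensitivity.

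A second reply is that the full protocol may hold visit-by-visit instructions that govern the fellow eye. That is possible, since Table 1, footnote 1, points to differences by visit, but it is an inference. Nothing in the text available sets such a condition.

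Four stronger readings are tempting, and the documents do not support them:
- *That c tells sites to ignore disease in the other eye.* Its silence does not override criterion q or Section 5.0.
- *That infection in the fellow eye is certainly uncovered.* This depends on which of the two readings of c is taken.
- *That a number of exposed subjects or extra adverse events can be stated.* Any such figure would only restate assumed rates, and would also assume that the existing safeguards stop no one.
- *That all study-eye limits are faulty.* Criteria b, d and n carry the same limit, but they mainly protect measurement in the analysed eye and are not in question.

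**Conclusion.** The point holds as a gap between two written rules. The plan allows product on a fellow eye without requiring that eye to be free of the conditions that c bars in the study eye. On the plain reading the gap covers acute infection and other active inflammation; on the narrower reading it covers only the latter. The finding rests on the text as provided containing all the rules on fellow-eye dosing.

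Severity is minor. The number of subjects cannot be estimated from the documents, and existing safeguards make the case unlikely. Efficacy is analysed in the study eye, so the primary analysis is not affected. The change is still worth making, because it removes an avoidable risk to patients at almost no cost.

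**What to change.** 1. Add to Section 4.2: *The non-study eye is dosed only if it has blepharitis and no acute ocular infection or other active ocular inflammation.* As a dosing rule, it applies whenever dosing of that eye begins.
2. Reword the end of exclusion c to: *in the study eye or any other eye to be dosed with IP.* Place it so that it clearly governs both infection and inflammation, which also settles the ambiguity.
3. State that the slit lamp examination at Visit 1 and Day 1 covers every eye to be dosed. It is already scheduled at both visits, so no visit or procedure type is added.

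The cost is that a few subjects will be dosed in one eye only or will fail screening. Extending c to either eye without qualification would be simpler to read, but it would also exclude subjects whose affected fellow eye would never be dosed. The wording above avoids that. Criteria b, d and n can stay as they are.

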4.0 STUDY TREATMENTS

4.1 Investigational Product

ISV-305 is a topical ophthalmic formulation of 0.1% dexamethasone in DuraSite 2. The vehicle utilized in this study is the same formulation as ISV-305 (i.e., DuraSite 2) without dexamethasone.

4.2 Instructions for Use and Administration

Subjects will be randomly assigned to receive either ISV-305 or vehicle which will be administered BID to the closed study eyelid and if needed to the closed non-study eyelid along the eyelash line as a topical ophthalmic: 1 drop per eye in the morning and 1 drop per eye in the evening for 14 days. Subjects (including parent and/or caregiver) will be instructed to smear 1 drop of IP to the closed study eyelid along the eyelash line on Day 1 at the study site upon randomization and 1 drop in the evening, and to continue dosing BID at approximately 12-hour intervals for a total of 14 days. Subjects will then be followed for an additional 15 days. Subjects will be given a dosing diary to record IP application times, and will be questioned to determine if they have followed the dosing schedule.

5.0 CONTRAINDICATIONS, WARNINGS AND PRECAUTIONS

Contraindications, warning and precautions for ophthalmic dexamethasone as described in the labeling of the approved product Maxidex (0.1% dexamethasone) are presented below.

Use of ophthalmic dexamethasone is contraindicated in epithelial herpes simplex (dendritic keratitis), vaccinia, varicella, and most other viral diseases of the cornea and conjunctiva, tuberculosis of the eye and fungal disease of ocular structures.

Class warnings for corticosteroids such as dexamethasone are well known and state that prolonged use may result in ocular hypertension and/or glaucoma, with damage to the optic nerve, defects in VA and fields of vision, and posterior subcapsular cataract formation. Prolonged use may also suppress the host response and thus increase the hazard of secondary ocular infections. In diseases causing thinning of the cornea or sclera, perforations have been known to occur with the use of topical corticosteroids. In acute purulent conditions of the eye, corticosteroids may mask infection or enhance existing infection. It is recommended that if corticosteroids are used for 10 days or longer, intraocular pressure should be routinely monitored even though it may be difficult in children and uncooperative patients.

The possibility of persistent fungal infections of the cornea should be considered after prolonged corticosteroid dosing.

Subjects are excluded from participating in the study if there is known hypersensitivity or poor tolerance to any component of the IP or any of the procedural medications such as anesthetic and/or fluorescein drops, dilating drops, etc. See Exclusion Criterion a.

